PROTOCOL

Title: diEtitiaNs Helping pAtieNts CarE for Diabetes (ENHANCED)

IRB number: 798246

Protocol Version: 1

Version Date: 6/25/2016

PI: [name]

Staff on study: [name], [name], [name], [name], [name], [name]

1. Study Synopsis:

This will be a randomized-controlled trial to examine the impact of a Registered Dietitian (RD) led telemedicine program on diabetes outcomes for adults with type 2 diabetes. Two groups will be compared over one year; an intervention group who receives the telemedicine program versus a control group who receives usual diabetes care. Specifically, we will assess the 'D5,' which is a set of five treatment goals that when reached together, represent the gold standard for managing diabetes. D5 outcomes includes the proportion of participants in each group who achieve goal levels for blood glucose, blood pressure, tobacco use, statin use, and aspirin use.

2. Background:

Diabetes is a progressive, complex disease that requires frequent follow-up and ongoing care. Five key metrics—blood glucose, blood pressure, tobacco use, statin use, and aspirin use – commonly referred to as the “D5” are targeted in individuals with diabetes to reduce the risk of health complications¹. A recent review found that some risk factors were generally improving in U.S. adults with diabetes (e.g. blood glucose, LDL cholesterol), but 30-50% still did not meet individualized targets for glycemic control, blood pressure, or lipid control, and more than 20% remained smokers².

Poor diabetes control is also evident at local levels, particularly where access to diabetes care and education is more limited. In Hutchinson, MN, a rural region about 60 miles west of the Minneapolis metropolitan area, diabetes care quality is below the state average. The same is true for New Ulm Medical Center (NUMC). According to Minnesota Community Measurement, 30% of Hutchinson Health’s diabetes population is at goal on all D5 measures and 39% for NUMC. The breakdown of individual D5 measures for diabetes patients in Hutchinson and NUMC, respectively include:

- Blood pressure <140/90 mmHg (81%, 87%)
- Statin use (83%, 64%)
- Glycated hemoglobin (A1C) <8% (46%, 68%)
- Not using tobacco (86%, 88%)
- Taking daily aspirin as appropriate (99%, 99%)

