Most diabetes care in the U.S. is delivered by primary care providers (PCPs), although it is well documented that PCPs face significant time constraints to address all health issues adequately. The National Standards for Diabetes Self-Management Education³ emphasize the importance of a multidisciplinary clinical care team, which includes a registered dietitian (RD), to reduce disease risks. The role of the RD is well established for nutrition, physical activity, and behavior change education with high risk patients, but the involvement of RDs in other aspects of diabetes care is more limited, particularly as it relates to medication management. The few studies in this area have found encouraging results. Robinson and colleagues demonstrated that RDs who followed a lipid-titration algorithm were able to double the number of patients meeting lipid goals⁴.

Worth and Davies found that RDs who recommended, monitored, and titrated lipid-lowering therapies were able to achieve significant improvements in both total cholesterol and triglycerides⁵.

Innovative models are clearly needed to complement usual diabetes care. Achieving blood pressure, lipid, and glucose goals in adults with diabetes requires extensive lifestyle counseling, patient education, and pharmacological therapy, with frequent follow-ups to address challenges as they arise. This study will examine the impact of an RD-led, primary care integrated, telemedicine program on the D5 measures over one year as compared to a usual care group that will receive usual care only during this timeframe.

3. Specific Aims

The specific aims of this study are to:

1. Compare individual and composite D5 optimal care measures between patients in the intervention group vs. those in the usual care group.
2. Analyze changes in secondary outcomes including nutrition, physical activity, body mass index, medication adherence and gender.

Methods

4. Subjects and Setting:

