Sample. We will seek to recruit 144 participants for this trial. Patients will be recruited from Hutchinson Health in Hutchinson, MN and New Ulm Medical Center in New Ulm, MN in order to reach our recruitment goal. Hutchinson Health is an independent hospital/clinic that contracts with Allina Health to use their EHR. New Ulm Medical Center is part of the Allina Health system. Eligible patients will be identified by Allina Health informatics personnel based on the most recent available information contained in the EHR. Only EHR data from the previous 2 years will be considered to determine eligibility. Data will be extracted from the EHR system to identify individuals who are seemingly eligible for this study based on the criteria listed below. Each individual's most recent value for each measure from the previous 2 years will be considered. Values greater than 2 years old will be considered missing. Inclusion criteria will be:

- Diagnosis of type 2 diabetes
- Meeting 0-3 of the D5 measures
- Individuals meeting 0 of the D5 measures and have no more than two missing measures
- Individuals meeting 1 of the D5 measures and have no more than one missing measure

- Age 40-75 years
- 'Homed' in the Hutchinson Health clinic. This is defined as having at least one ambulatory care visit at the Hutchison Health clinic in the last 2 years.
- 'Homed' at the New Ulm Medical Center. This is defined as having at least one ambulatory care visit at NUMC in the last 2 years.

Exclusion criteria:

- Individuals meeting ≥ 4 D5 measures
- Individuals meeting ≥ 2 D5 measures with any missing measures
- Type 1 diabetes
- Chronic kidney disease (GFR <30)
- HIV
- Institutional residence
- Major cognitive or language barrier (as determined by program enrollment staff)
- Other active end-stage disease (e.g., late stage cancer or pulmonary disease)
- Actively receiving cancer treatment
- Pregnant

Study Recruitment

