Recruitment will be conducted over a four to six month timeframe beginning in late 2015 and will start with Hutchinson Health. Once recruitment efforts are exhausted in Hutchinson, the same process will occur at New Ulm Medical Center. Contact information for study-eligible individuals will be extracted from the Hutchinson Health and New Ulm Medical Center/Allina Health EHR. A random sample of these enumerated individuals will be drawn and an initial letter will be mailed, signed by their PCP that contains a description of the study and an invitation to contact the study team by phone for eligibility screening. Up to three additional outreach attempts by phone will be made until a response is received. The screening phone call will confirm study eligibility and the baseline study (enrollment) visit will be scheduled with a study team member. Patients will be instructed to fast prior to their baseline visit in order to obtain accurate lab values.

Baseline study visit

- At the baseline visit, patients will be provided with study related information and have an opportunity to ask questions. Study personnel will verify inclusion/exclusion criteria to confirm eligibility. If subjects meet study criteria, they will be consented to participate in the study. The baseline visit will be completed in-person for all participants and will be led by a study coach with the assistance of lab personnel. They will last 30-45 minutes and include detailed study explanation and consent, completion of baseline lifestyle survey, measurement of anthropometrics, and a blood draw (described further below). In addition, a brief education session with a study coach will be conducted and focused on optimal diabetes measures and basic diabetes nutrition and physical activity recommendations. Individuals will also receive a diabetes basics booklet from the International Diabetes Center. Randomization will take place at the end of the visit using a 5 block envelope; an equal number of participants will be randomly assigned to the intervention and control groups. For those randomized to the intervention group, the first phone appointment will be scheduled upon completion of the baseline visit.

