Coaches in this study will be registered dietitian/certified diabetes educators trained to address the D5 optimal care measures. They will also be trained in the use of a medication protocol that permits initiation and titration of blood glucose, lipid, and/or blood pressure medications (attachment). All coaching aside from the baseline and final visits is done via telephone and participants will generally receive a minimum of one call per month. The intervention is designed to complement to usual clinic-based primary care, with coaches documenting lab, biometrics, and medication adjustments in the EHR, along with documenting phone encounters and communicating directly with patients' PCPs as needed.

Documentation in the EHR uses an order created specifically for the study indicating the patient's research status; "opt-in" for those who choose to enroll.

To answer outcome evaluation questions, all individuals with a diabetes research study order will be extracted from the EHR along with baseline and 12 month D5 measures collected during respective visits. For comparisons between the intervention and usual care patients, the analysis

will examine mean changes in biometric risk factors and the percentage of patients meeting recommended levels for the D5 measures at baseline and after the one year intervention period. Medication changes will also be examined and compared between the two groups.

Study procedures will be approved in advance by the Allina Institutional Review Board.

Analysis

Analyses and power. A moderate effect size is expected of at least (Cohen's $w=0.25$) in this trial. Over one year, this translates into about 30% of the intervention group experiencing improvement in ≥ 1 D5 measure vs. 10% of usual care participants. Under the assumptions of 85% power, an alpha-level of 0.05, and a one degree of freedom test, 144 total participants (72 in each group) will be needed for this study. Mixed regression models will be used to compare D5 outcomes between the two study groups over time. Similar analyses will be conducted on secondary outcomes as well. An intent-to-treat framework will be used that will include all randomized participants.

6. Risk/ Safety information

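### Compare the all-five D5 composite between arms at 12 months, and adjust biometrics for baseline, instead of analysing change over time: a no-cost improvement

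*Combined protocol and SAP*

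**What the plan says.** Aim 1 (section 3) is to "Compare individual and composite D5 optimal care measures between patients in the intervention group vs. those in the usual care group". The composite is given no operational definition. Two places point to all five goals met. The Synopsis calls the D5 "a set of five treatment goals that when reached together, represent the gold standard for managing diabetes", and the Background reports that 30% of Hutchinson Health's "diabetes population is at goal on all D5 measures and 39% for NUMC".

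Section 4 admits patients "Meeting 0-3 of the D5 measures" and excludes "Individuals meeting ≥ 4 D5 measures". Screening rests on health-record values: "Only EHR data from the previous 2 years will be considered to determine eligibility". At the baseline visit, "Study personnel will verify inclusion/exclusion criteria to confirm eligibility", but how D5 status is rechecked is not described.

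The Measures paragraph makes changes in the D5 measures primary, assessed at baseline and 12 months, with interim and unavailable values taken from the health record where possible. Section 5 adds that average changes in biometrics will be compared, and that the percentages at goal will be examined at baseline and at one year. The only statement of a model is "Mixed regression models will be used to compare D5 outcomes between the two study groups over time". The sample size uses a different quantity, improvement on at least one measure (30% vs 10%).

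**The concern.** The entry rule fixes the starting value of the composite. Nobody can be at five of five on the screening values. The missing-value rules cannot hide such a patient either, because two or more goals met with any value missing is an exclusion. Only drift since a record up to two years old can put someone at five of five by the baseline visit.

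When baseline is constant or nearly so, subtracting it removes almost no between-patient variation. A contrast of changes then carries the sampling noise of two visits where one would do. On the logit scale it is worse, because the log-odds of a near-zero proportion is very imprecise and at zero does not exist. If that model were chosen and failed, the analyst would have to pick another after seeing the data. Comparing average changes in continuous biometrics also gives up precision that a baseline-adjusted analysis keeps.

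**Working it through.** **The plan's own figure.** Rates of 30% vs 10% give w = 0.25. N = ((1.960 + 1.036)/0.25)² = 143.7, so 144, with 85.1% power. The figure reproduces. It belongs to a one-degree-of-freedom comparison of two proportions for improving on at least one measure, and nothing below changes it.

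**Illustrative composite rates.** The documents give all-five rates for whole clinic populations (30% and 39%), not for entrants. Anyone newly reaching five of five has improved on at least one measure, so the planned 30% vs 10% is roughly an upper bound for each arm. Entrants lack at least two goals on screening values, so true rates are probably lower.

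**One worked example, 72 per arm: 22 vs 7 at 12 months.**
- 12-month log odds ratio = ln(22/50) − ln(7/65) = 1.407. SE = √(1/22 + 1/50 + 1/7 + 1/65) = 0.473, p = 0.003.
- Logistic group-by-time term with b patients per arm at five of five at baseline: same estimate, SE = √(0.473² + 2(1/b + 1/(72−b))). For b = 1, 2, 3 the SE is 1.501, 1.119, 0.959 and p = 0.35, 0.21, 0.14.
- For b = 0 in both arms, group and time terms alone already fit all four cells, so the likelihood-ratio (LR) statistic for the interaction is 0 whatever happens at 12 months.

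**Power** (72 per arm, two-sided 5%, visits independent, 200,000 simulated trials; baseline proportion 2/4/6/10%):

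| 12-month rates | Logit interaction, Wald | Logit interaction, LR | Identity-link change | 12-month only, Wald; LR |
|---|---|---|---|---|
| 30% vs 10% | 0.08/0.23/0.34/0.46 | 0.20/0.29/0.36/0.47 | 0.83/0.79/0.75/0.70 | 0.86; 0.87 |
| 15% vs 5% | 0.04/0.14/0.20/0.26 | 0.18/0.23/0.27/0.32 | 0.46/0.40/0.36/0.31 | 0.45; 0.54 |

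At 6% vs 2%, the 12-month LR test has about 30% power.

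Four qualifications apply.
- Trials with an empty cell count as Wald failures. At 2% baseline the chance that at least one arm is empty is 1 − (1 − 0.98⁷²)² = 41%, so the low end is partly a test artefact.
- The LR interaction rejects in 5.5-7.3% of null trials, so part of its gain over Wald is inflated size.
- Within-person correlation helps the change tests. With phi 0.3 (capped at the feasible maximum), the Wald interaction has 10-60% at 30% vs 10%. With latent correlation 0.5, the identity-link test has 88% at 2% baseline and 80% at 10%, against 87-88% for the 12-month test.
- These are marginal models, not random-intercept fits.

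**Aspirin.** Both clinics report 99% at goal. Assume the five measures are independent and entrants resemble clinic patients meeting at most three goals.
- Share meeting at most three goals: 26.6% (Hutchinson) and 23.2% (New Ulm).
- Hutchinson, share of these off aspirin goal: 0.01 × (1 − 0.81×0.83×0.46×0.86)/0.266 = 2.8%.
- New Ulm: 0.01 × (1 − 0.87×0.64×0.68×0.88)/0.232 = 2.9%.
- Out of 72, that is about 2 per arm.

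Independence is only rough: it gives all-five rates of 26% and 33%, against the stated 30% and 39%.

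**Continuous biometrics.** With equal variance σ² at both visits and correlation ρ, the change-score variance is 2σ²(1−ρ) and the ANCOVA variance is σ²(1−ρ²). The ratio is (1+ρ)/2: 0.80 at ρ = 0.6 and 0.70 at ρ = 0.4. Both values of ρ are assumed; the documents give none.

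**The case against.** The strongest reply is that the plan names no logit link and no interaction. Linear, common-baseline, 12-month-only and goal-count analyses all fit its wording and avoid the collapse. Section 5 already says that percentages at goal will be looked at after one year, and the power statement is a simple test of two proportions. This stands. A reader might infer that the planned analysis is bound to fail, but the documents do not support that. They show an open choice, one version of which would fail.

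Second, the composite appears in Aim 1 but not in the list of primary outcomes or in the sample size. That also stands, and it limits the weight of the point.

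Third, the 30% vs 10% illustration is favourable to the 12-month test. Every entrant needs about two or more gains to reach five of five, while the plan expects only 30% vs 10% to make even one. This stands too. A reader might infer that moving to 12 months makes the composite adequately powered, and the lower rates above show that it does not.

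Fourth, ANCOVA is a separate matter. It is a gain in precision, not a correction of bias, but it replaces a comparison that the plan does state and costs nothing.

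**Conclusion.** This is a free improvement, not a demonstrated error. For a composite that starts at or near zero by design, a 12-month between-arm comparison is the better test. At the illustrative upper bound it has 86-87% power, against 83-70% for an identity-link change test and 8-46% (Wald) for a logistic interaction over 2-10% at baseline. The margin over the identity-link test vanishes at exactly zero baseline and shrinks when visits are strongly correlated. At 15% vs 5% and below, no test has adequate power, and the composite should not be presented as if it did.

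The conclusion rests on reading the composite as all five goals met, on assumed 12-month rates, and on an assumed 0-10% at the baseline visit. It would be wrong to infer that N=144 or the at-least-one-measure rate is affected. It would be equally wrong to infer that all individual goals are safe from the same problem, since aspirin may have a sparse cell at the other end of the scale.

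**What to change.** Amend the analysis paragraph of section 5 as follows.

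1. Define the composite as all five D5 goals met (yes/no). Compare it between randomised arms at 12 months by logistic regression with a likelihood-ratio test, or as a risk difference with robust standard errors, adjusted for baseline D5 count. Include all randomised participants, with the health-record values already planned for those unavailable at follow-up. Report it without a claim of adequate power.
2. Use the same 12-month comparison for any individual goal with few patients off goal at baseline, such as aspirin. A mixed model can stay for the other goals if its link, time points and tested term are stated.
3. Analyse continuous biometrics by ANCOVA on the 12-month value, adjusted for the baseline value, in place of average changes.

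The cost is wording only. Baseline and 12-month values are already collected, and the sample size does not change.

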This study is minimal risk because the only risks associated with this study are: 1) Potential identification of individuals; 2) Individuals may be uncomfortable answering certain questions in the questionnaire; and 3) Potential risk associated with venipuncture at baseline and 12 month visit; 4) patient may experience adverse side effect from being started on a blood pressure, statin, or diabetes (blood glucose) medications. However, all of the medications on the protocol are currently used in diabetes care standards of practice (none are investigational).

1. To mitigate this risk, the study personnel with access to this data already have access to similar types of data for their work and have procedures in place to limit access to this identifying information. Data is stored in a secure folder at Allina, and patient identifiers will be eliminated from data sets after appropriate analysis is done.
2. Study participants can choose not to answer any questions in the questionnaire that may make them uncomfortable.
3. Venipuncture: There are minor risks associated with drawing blood. Participants may feel brief pain, develop a bruise, become lightheaded, or faint. In rare cases, an infection may occur.
4. Medication protocol: Any medications prescribed by the RD/Phone coach will require a co-signature by the patient's primary care provider or medical director. This intervention poses no more risk than going to a primary care provider for diabetes care management. The protocol also has indications for assessment and action for those who experience side effects (see Diabetes Medication Protocol appendix).

7. Monitoring / Reporting of AE/ SAE

ENHANCED 798246

We believe this study poses no more than minimal risk and as such do not expect any safety events. The main risk with this type of study is potential identification of individuals included in the study, risk associated with venipuncture or an adverse reaction to a medication. Only individuals on the study research team will see the individual level data in this study. If there is a breach of confidentiality, those people will work together to report it to the compliance office and IRB and follow the appropriate procedures. However, we will follow all standard procedures to ensure data privacy is maintained by storing data in a limited access folder that is on the Allina servers.

8. Study Oversight

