We do not foresee any conditions under which this study would be prematurely terminated as the risks associated with participating in the diabetes research project are minimal and include no more risk than usual care. If the study is prematurely terminated, the study will be made available for monitoring, auditing, IRB review and regulatory inspection by providing direct access to study related source data.

9. Data Management

The diabetes research study database will be maintained by the MHIF team and a final research data set will be created which will be managed by team members from Allina Health who maintain this data as part of their routine job responsibilities. All analysis will be done in SPSS by members of the research team. Data will be maintained in a limited access folder on Allina Servers.

10. IRB Review/ Ethics/ Informed Consent

The protocol and relevant supporting information must be submitted to the IRB for review and must be approved before the study is initiated. In addition, any subject recruitment materials must be approved by the IRB prior to being used. This study will be conducted in accordance with the ethical principles that have their origin in the Declaration of Helsinki and that are consistent with Good Clinical Practice and applicable regulatory requirements. The study must be conducted in accordance with applicable regulations, applicable laws and the IRB requirements. The Sponsor must submit any change to the protocol to the IRB for review and approval before implementation.

11. Confidentiality

Only 5 people will have access to identifying data through this study. Two are Allina employees who work with patient data for research purposes as part of their job and as such will follow standard procedures for protecting data privacy. The other three are employees of the Minneapolis Heart Institute Foundation who oversees the HBC program. Through a contractual agreement between Allina and MHIF, this person

has access to the Allina EHR and has access to patient data related to the HBC program. Data is stored in a secure folder at Allina with access limited to the people doing analysis and the health informatics person pulling data out of the EHR, and patient identifiers will be eliminated from data sets after data cleaning and analysis is done. All study records identifying the subjects will be kept confidential and will not be made publicly available or presented in any publications.

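### The AE/SAE section gives a reporting step only for confidentiality breaches, so drug reactions, emergency visits and admissions have no planned by-arm count or reporting route although dietitians start and titrate drugs

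*Combined protocol and SAP*

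**What the plan says.** Section 6 (Risk/ Safety information) gives as its fourth risk that a "patient may experience adverse side effect from being started on a blood pressure, statin, or diabetes (blood glucose) medications". It answers this with a safeguard, "Any medications prescribed by the RD/Phone coach will require a co-signature by the patient's primary care provider or medical director", with a reference to a medication appendix that covers what to do about side effects, and with an assurance: "This intervention poses no more risk than going to a primary care provider for diabetes care management".

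Section 7 (Monitoring / Reporting of AE/ SAE) opens with "We believe this study poses no more than minimal risk and as such do not expect any safety events". The next sentence names the main risks as identification of participants and "risk associated with venipuncture or an adverse reaction to a medication". One reporting step follows: "If there is a breach of confidentiality, those people will work together to report it to the compliance office and IRB". The rest of the section is about data privacy.

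Section 8 (Study Oversight) foresees no condition for early termination, on the ground that the risks are minimal and "include no more risk than usual care".

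Sections 4 and 5 make drug management part of the intervention. The coaches are dietitians who work by telephone under an attached protocol and may start and adjust drugs in three classes: glucose, lipid and blood pressure.

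**The concern.** Section 2 describes dietitian involvement in medication management as limited and the studies of it as few. That makes drug management the part of the intervention where harm most needs counting. The section that should say how this is done says instead that no events are expected. It gives no definition of an adverse or serious adverse event, no collection schedule, and no route or timeline for reporting a drug reaction.

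At stake is the balance of the published result. The trial could report more patients reaching D5 goals without a systematic count of drug reactions, emergency visits or admissions to set beside it. The primary D5 comparison itself is not affected.

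**Working it through.** **1. What is listed as a risk, and what has a reporting step**

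- Identification of participants: a risk in Sections 6 and 7; reporting step to the compliance office and IRB in Section 7.
- Drug reactions: a risk in Sections 6 and 7; no reporting step in Section 7.
- Venipuncture: a risk in Sections 6 and 7; no reporting step in Section 7.

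**2. What would already be compared by arm**

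- Hypoglycemia is a self-reported frequency item in the outcome table at the end of the protocol. Section 4 (12-month/Final visit) repeats the baseline measures, without restriction by arm. Section 5 (Analysis) extends the between-group models to secondary outcomes and includes everyone randomised. Together these allow a two-arm comparison of hypoglycemia. The prose list of secondary outcomes in Section 4 does not name it.
- Section 5 also compares D5 measures, biometric changes and medication changes.
- Statin and blood pressure drug reactions, emergency visits and admissions appear in none of these.

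**3. The plan's own figure**

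The inputs from Section 5 (Analysis) are 30% against 10%, w = 0.25, 85% power, alpha 0.05 and 1 df.

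- w = 0.20 / (2 × √(0.20 × 0.80)) = 0.25.
- N = (z₀.₉₇₅ + z₀.₈₅)² / w² = (1.9600 + 1.0364)² / 0.0625 = 143.65, rounded up to 144, or 72 per arm.

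The figure reproduces. It is an efficacy figure; the plan states none for safety.

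**4. What 72 per arm could say about harm**

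The documents give no adverse-event rates, so those below are assumed. Full follow-up is also assumed.

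- Zero events in one arm: upper limit = 1 − 0.05^(1/72) = 4.1% one-sided, or 1 − 0.025^(1/72) = 5.0% two-sided.
- Chance of seeing at least one event in 72, from 1 − (1 − p)^72: 51.5% at p = 1%, 76.7% at 2%, 97.5% at 5%.
- Half-width of the 95% interval for the difference between arms, from 1.96 × √(2p(1 − p)/72): ±4.6 points at p = 2%, ±7.1 at 5%, ±9.8 at 10%.
- Participants per arm needed to exclude a 5-point excess (80% power, one-sided 0.025), from (1.9600 + 0.8416)² × 2p(1 − p) / 0.05²: 124 at p = 2%, 299 at 5%, 566 at 10%.

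At each of these three rates, the number needed is above 72. Full recording would therefore support a description of harm by arm, not a test of equal risk.

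**The case against.** A reader might infer more than the documents support, in four ways.

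- **That hypoglycemia would go uncounted.** It would not, as step 2 of the working shows. The limit is that it is one recalled item, is not designated a safety measure, and cannot capture reactions to statins or blood pressure drugs or serious events.
- **That drug reactions would be neither recorded nor reported at all.** Coaches document medication adjustments and phone encounters in the EHR and contact primary care providers as needed. Calls include a medication assessment and may be more frequent when a drug is started. Prescriptions are co-signed. The medication appendix covers side effects; it is not in the supplied text, so what it says about documentation or escalation is unknown and its absence is not held against the plan. Section 10 commits the study to Good Clinical Practice and IRB requirements. These are real safeguards for the individual patient. None, as described, is a count by arm or a stated AE/SAE reporting route.
- **That the trial fails to test its own claim of no added risk.** That statement justifies minimal-risk status; it is not a hypothesis. Section 12 gives the purpose as measuring D5 changes. The weakness is that the statement is asserted without data and then used in Section 8.
- **That Sections 6 and 7 strictly contradict each other.** Listing a possible risk while expecting no events is loose drafting. It matters because the reporting plan appears to follow the expectation and not the risk list.

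It is also fair to say that the drugs are in standard use and not investigational. That does not settle the matter, because what differs between arms is who starts and adjusts them, and how.

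**Conclusion.** The concern holds in this form: followed as written, the plan has no by-arm count of drug reactions other than hypoglycemia, or of emergency visits or admissions, and states no reporting route for them. Hypoglycemia can be compared by arm, and clinical handling of side effects exists.

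The change is worth making but leaves the primary analysis untouched. Its reach is limited: with 72 per arm, even zero events leaves a one-sided 95% upper limit of 4.1%, and that bound concerns one arm, not the difference between arms. The comparison can only be descriptive. The figures for differences rest on assumed event rates of 2% to 10% and complete follow-up; losses would widen them.

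**What to change.** - In Section 7, replace the sentence that no safety events are expected with a descriptive safety table by arm for all randomised participants. Use the existing 12-month hypoglycemia item plus EHR-extracted emergency visits, admissions and recorded drug reactions, from the same sources in both arms.
- List reactions detected by coaches on calls separately, because controls receive no calls.
- Extend the existing IRB reporting route to these events, with definitions and a timeline.
- In Sections 6 and 8, word the statements on risk relative to usual care as an expectation, since this sample cannot establish them.

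The cost is a few more EHR fields, one table and minor coach documentation, with no extra visits. One weakness remains. Coaches write in the EHR, so recorded drug reactions may be captured more fully in the intervention arm. Emergency visits and admissions are the fairer comparison, and the table should say so.
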